PASS INFORMATION

Study title	Drug utilisation study of Intuniv® (guanfacine extended release) in European Countries – A prescriber survey		
Protocol Version identifier	Version 5.0 17 July 2018		
Date of last version of protocol	Version 4.0 12 June 2018		
EU PAS Register number	EUPAS18739		
Active substance	Guanfacine (ATC code: C02AC02)		
Medicinal product	Intuniv [®]		
	Marketing authorisation numbers:		
Product reference	 1mg: EU/1/15/1040/001-002 2mg: EU/1/15/1040/003-005 3mg: EU/1/15/1040/006-007 4mg: EU/1/15/1040/008-009 		
Procedure number	EMEA/H/C/03759		
Marketing authorization holder (MAH) or sponsor company	Shire Pharmaceuticals		
Joint PASS	No		
	Research question:		
Research question and objectives	Implementation of a multi-country drug utilization study for up to 5 years with Intuniv® and provision of data on an annual basis in up to 10 European countries. In Belgium, Finland, Ireland and Netherlands data on the use of Intuniv® will be collected within a prescriber survey which is described in this protocol. In other countries a database analysis will be performed which is described in a separate protocol.		
	Study objectives:		
	Primary objectives:		
	To characterize patients who are prescribed Intuniv [®] with a specific focus on		
	o Indications other than ADHD		
	o Children less than 6 years of age		

	o Adults				
	 Patients who did not have any first-line stimulant treatment prior to their first prescription of Intuniv[®] 				
	o Prescribed overdose of >7 mg/day or of >4 mg/day for patients ≤12 years of age				
	To describe prescribing patterns of Intuniv [®] among physicians				
	Secondary objective:				
	To describe the effectiveness of the additional risk minimisation measure (educational materials for healthcare professionals) in order to assess compliance with the indication and with visits and measurements needed during the first year of treatment				
Countries of study	Belgium, Finland, Ireland, Netherlands				
Author	IQVIA , PhD, , , RWES/HEOR [name]; email:				
MAH(s)	Shire Pharmaceuticals Shire Pharmaceutical Contracts Limited [name]				
	UNITED KINGDOM				
MAH contact person	, PhD Shire Pharmaceuticals Outcomes Research & Epidemiology [name]				
	~~				

IQVIA is a partner centre of the ENCePP scientific network which is coordinated by the European Medicines Agency. IQVIA is dedicated to excellence in research by adhering to the ENCePP Guide on Methodological Standards and promoting scientific independence and transparency.

2. ABBREVIATIONS

Abbreviation	Definition		
ADHD	Attention deficit hyperactivity disorder		
AE	Adverse event		
AR	Adverse reaction		
ASOCS	Association of Opinion and Behaviour in health field research companies		
СНМР	Committee for Medicinal Products for Human Use		
CI	Confidence interval		
EC	Ethics committee		
EMA	European Medicines Agency		
ENCePP	European Network of Centres for Pharmacoepidemiology and Pharmacovigilance		
EphMRA	European Pharmaceutical Marketing Research Association		
GVP	Good pharmacovigilance practices		
GP	General practitioner		
НСР	Health care professional		
IR	Immediate release		
MAH	Marketing authorization holder		
MR	Modified release		
PASS	Post-authorization safety study		
PRAC	Pharmacovigilance Risk Assessment Committee		
PSUR	Periodic safety update report		
RMP	Risk minimization plan		
SAE	Serious adverse event		
SAP	Statistical analysis plan		
SAR	Serious adverse reaction		
SOP	Standard operating procedures		
SmPC	Summary of product characteristics		
STROBE	Strengthening the reporting of observational studies in epidemiology		

4.2 Rationale and background

Shire Pharmaceuticals has launched or plans to launch Intuniv[®] in Belgium, Denmark, Finland, Germany, Ireland, Netherlands, Norway, Portugal, Spain, Sweden and UK from January 2016 onwards. Intuniv[®] is indicated for the treatment of attention deficit hyperactivity disorder (ADHD) in children and adolescents 6 to 17 years old for whom stimulants are not suitable, not tolerated or have been shown to be ineffective (1). Shire Pharmaceuticals will conduct a drug utilization study as part of the risk management plan for Intuniv[®] in Europe.

In Belgium, Finland, Ireland, and the Netherlands, data on the use of Intuniv[®] will be collected within a prescriber survey which is described in this protocol. In other countries a database analysis will be performed which is described in a separate protocol (Annex 1).

4.3 Research question and objectives

Research question:

The study's overall research question and objective is to characterize patients who are prescribed Intuniv[®], to describe prescribing patterns among physicians and to evaluate if additional risk minimisation measures that had been provided to physicians were successfully implemented and effective. Data on use of Intuniv[®] will be provided on an annual basis for up to 5 years in up to 12 European countries. In Belgium, Finland, Ireland, and Netherlands, data on the use of Intuniv[®] will be collected within a prescriber survey which is described in this protocol. In other countries a database analysis will be performed which is described in a separate protocol.

Study objectives:

Primary objectives:

- To characterize patients who are prescribed Intuniv[®] with a specific focus on
 - o Indications other than ADHD
 - o Children less than 6 years of age
 - Adults
 - o Patients who did not have any first-line stimulant treatment prior to their first prescription of Intuniv®
 - o Prescribed overdose of >7 mg/day or of >4 mg/day for patients ≤12 years of age

• To describe prescribing patterns of Intuniv® among physicians

Secondary objective:

 To measure the effectiveness of the additional risk minimisation measure (educational materials for healthcare professionals) in order to assess compliance with the indication and with visits and measurements needed during the first year of treatment

4.4 Study design

This is a multinational, cross-sectional, non-interventional and anonymous survey carried out among physicians who will be asked to provide de-identified patient data. The survey will be conducted through a web-questionnaire among prescribers of Intuniv® in four European countries (Belgium, Finland, Ireland, and Netherlands).

4.5 Population

Patients who have been prescribed Intuniv ® at least once during the study period.

The survey will be conducted annually from 2019 to 2022 among prescribers, or potential prescribers, of Intuniv[®] representative for the selected countries (Belgium, Finland, Ireland, and Netherlands). The physicians will be instructed to select the most recent patient records, for patients for who at any time in the last 12 months (or, for the first report, since country specific launch) they have prescribed Intuniv[®] (whether or not Intuniv[®] was prescribed at that last visit).

1 to 10 patients per physician may be reported, with the most recent patients being reported first.

4.6 Variables

The collected information includes:

- Physician related data (demographics, setting, prescriber's specialty)
- Drug utilization data: indication of use/diagnosis, patient characteristics (age, gender, comorbidities), data on patterns of drug use (dosing, first time user, repeat user, duration, discontinuation of ADHD therapy and switches), frequency of monitoring and weight, blood pressure, heart rate if information is available.

4.7 Data sources

The survey will collect data from the following data sources:

- Physicians files (OneKey lists) for gender, specialty and region
- Data collected through a web questionnaire, including de-identified patient data provided by a representative sample of physicians known to treat patients with ADHD – predominantly paediatricians, psychiatrists, neurologists and GPs (representatively selected throughout the participating countries)

4.8 Study size

Per country and year, the target is to collect anonymous data of 50 to 100 patients, who have been prescribed Intuniv[®] at least once during the study period. Data will be provided by representative physicians qualified to treat patients with ADHD.

4.9 Data analysis

All analysis will be descriptive in nature and no statistical comparison will be done in this study. Results will be presented by country.

4.10 Milestones

Milestone	Planned date
Start of data collection (fieldwork) for	01 February 2019
first survey report, expected duration	
two months	
End of data collection (fieldwork) for	31 March 2022
last survey report	
Registration in the EU PAS register	26 April 2017
First survey report	30 June 2019
Second survey report	30 June 2020
Third survey report	30 June 2021
Last survey report	30 June 2022

5. AMENDMENTS AND UPDATES

Number	Date	Section of the study protocol	Amendment or update	Reason
Original protocol Version 1.0	16 Dec 2016	New protocol	nap	nap
Amended protocol, Version 2.0	19 Dec 2017	Throughout the document	Update the name of the subcontractor QuintilesIMS to IQVIA	Name change of company
		Page 1 of document	Update of address of the subcontractor	Office was moved
		Section 6: Milestones	Added launch date of Intuniv [®] in Spain	Launch date is available now and Intuniv [®] was

		launched in Spain
Section 7: Rational and background	Expanded rationale of the study	Recommended to justify the need for the study and the assessment of the risk minimisation measures
Synopsis and Section 8	Reworded research question	Rewording was done to align more with the objectives of the study
Section 9.1: study design	More detailed description of the study design and reference to the statistical analysis plan	To allow a better understanding of the study design
Synopsis and Section 9.2: Setting	Specified how recruitment for the survey will be done	For clarification of the setting and describe how representativeness is planned to be achieved
Section 9.3: variables	A reference to the SAP was made	For clarification that a detailed description and definitions of all variables are given there
Section 9.4: Data sources	Addition of questions was described	to assess knowledge of physicians regarding the risk minimisation measures were added to the questionnaire
Section 9.7.3 Questionnaire analysis	Hypothesis was added and description on how successful implementation of the risk minimisation	To include a process indicator that allows to measure if knowledge of the physicians with respect to the

			measures would be assessed.	educational material is adequate.
		Appendices	List of stand alone document was amended	For completeness
Amended protocol,	18 May 2018	Title page	Update of MAH contact	New MAH contact
Version 3.0		Throughout the document	Removal of France and Switzerland	Intuniv® not likely to launch in France and Switzerland in sufficient time for this study.
		Section 4.3: Research question and objectives	Update of study objectives	Harmonization of study objectives and criteria for off-label use.
		Section 6: Milestones and throughout the document	Update of milestones and reporting dates	Data collection period and reporting dates adapted according to expected protocol endorsement by the PRAC.
		Section 7: Rationale and background	Rewording of criteria for off-label use	Harmonization of study objectives and criteria for off-label use
		Section 8.2: Objectives	Update of study objectives	Harmonization of study objectives and criteria for off-label use.
		Section 9.2.1.	Clarification of inclusion criterion	Clarification that for the first report, patients who have received Intuniv [®] since the country specific launch date may be included
		Section 9.7.1:	Update of tables	Fieldwork and

		General statistical observations	and text	observation period adapted to new reporting dates.
		Section 9.8: Quality control	Update of SOPs in accordance with the IQVIA system	Due to the restructuring of the company to IQVIA the numbering system of SOPs and policies had been changed.
		14: Appendix	Update of table	New versions of stand-alone documents available.
Amended protocol, Version 5.0 17 July 2018	•	Section 7: Rationale and background	Text added	Clarification that Intuniv® is indicated as second line treatment
		Section 9.7.3: Questionnaire analysis	The predefined percentage to conclude effectiveness of aRMM was increased.	To into account the risks intended to be managed.
		14: Appendix	Update of table	New versions of stand-alone documents available.

6. MILESTONES

Table 1: Milestones

Milestone	Planned date
Start of data collection (fieldwork) for	01 February 2019
first survey report, expected duration	
two months per year	
End of data collection (fieldwork) for	31 March 2022
last survey report	
Registration in the EU PAS register	26 April 2017
First survey report	30 June 2019
Second survey report	30 June 2020
Third survey report	30 June 2021
Last survey report	30 June 2022

A survey report including the results for each of the four target countries will be provided annually. In total four reports will be prepared in frame of current study. The first report is planned for June 2019. The last report is planned for June 2022. The first survey will ask physicians to provide data on patients from the launch of Intuniv until the conduct of the survey, a period which could be longer than 1 year depending on the country. As such, the four reports provided will provide approximately five years of data. For country specific reporting schedule please refer to Table 2.

Table 2: Planned launch and reporting date by country (as of September 2016)

Country	Launch date	Report	Report	Report	Report
	of Intuniv®	30 Jun	30 Jun	30 Jun	30 Jun
		2019	2020	2021	2022
Belgium**	1 Nov 2016	X	X	X	X
Denmark ⁺	18 Jan 2016	X	X	X	X
Finland**	15 May 2016	X	X	X	X
Germany ⁺	15 Jan 2016	X	X	X	X
Ireland**	02 May 2016	X	X	X	X
Netherlands**	01 Nov 2016	X	X	X	X
Norway ⁺	15 May 2016	X	X	X	X
Spain ⁺	Jan 2017	X	X	X	X
Sweden ⁺	15 Feb 2016	X	X	X	X
UK ⁺	01 Feb 2016	X	X	X	X

^{**}country where survey is planned; +country where database study is planned

7. RATIONALE AND BACKGROUND

Attention Deficit Hyperactivity Disorder (ADHD)

ADHD is a developmental disorder (2). It is primarily characterized by the co-existence of attentional problems and hyperactivity, with each behaviour occurring infrequently alone and several inattentive or hyperactive-impulsive symptoms present prior to age 12 (2, 3). ADHD is the most commonly studied and diagnosed psychiatric disorder in children, affecting about 3 to 5 percent of children globally (4-6) and diagnosed in about 2 to 16 percent of school aged children (5). ADHD is a lifetime disorder (7) with 30 to 50 percent of those individuals diagnosed in childhood continuing to have symptoms into adulthood (7, 8). These symptoms include significant social, emotional and academic problems, low self-esteem, poor peer relationships, delinquency and substance abuse (5).

Causes of ADHD

The exact causes of ADHD are not known, although many studies suggest that there is a large genetic influence (9). Like many other psychiatric illnesses, ADHD results from a combination of factors. In addition to genetics, scientists are investigating possible effects of environmental factors, brain injuries, nutrition and the social environment on the development of ADHD (10).

Treatment of ADHD

Currently available treatments focus on reducing the symptoms of ADHD and improving functioning. Treatments include medication, various types of psychotherapy, education or training, or a combination of treatments.

Most commonly, ADHD is treated with stimulant medications, which are designed to have a calming effect on children with ADHD. Different types of stimulant medications are available, such as methylphenidate (e.g. Ritalin®, Concerta®), dexamphetamine (e.g. Attentin®) and lisdexamfetamine (e.g. Elvanse®). In general, their mechanism of action is on catecholaminergic neurons in the brain and ultimately leads to an increase of extracellular dopamine and norepinephrine levels in the prefrontal cortex (11).

Nonetheless, a subset of ADHD patients will either fail to respond to stimulants or have side effects that preclude their use (tics, severe loss of appetite, marked insomnia). For such patients, non-stimulant agents (like atomoxetine, trade name Strattera®) serve as second-line treatment.

Stimulants have been available for decades in Europe. The first non-stimulant medication was approved in the United Kingdom in 2004, and in Germany in 2005. In 2009, Shire Pharmaceuticals has launched a novel non-stimulant drug in USA and Canada: extended-release guanfacine (Intuniv®). Intuniv® is a long-acting, once-daily formulation of guanfacine (a selective alpha-2A-adrenergic receptor agonist) indicated for treatment of ADHD in 6 to 17 year old children and adolescents. It is indicated as a second-line treatment for patients for whom stimulants are not suitable, not tolerated or have been shown to be ineffective. As listed in the SmPC, Intuniv is indicated for the treatment of ADHD in children and adolescents 6-17 years old for whom stimulants are not suitable, not tolerated or have been shown to be ineffective.

Intuniv[®] can be prescribed as monotherapy and as adjunctive therapy to stimulant medications. Intuniv[®] has demonstrated improvement of a range of ADHD symptoms that can

be disruptive, such as inattention, hyperactivity, impulsivity, and extensive loss of temper (12). Intuniv[®] is not a controlled substance, which sets it apart from most other ADHD drugs. The active compound of Intuniv[®], guanfacine, is also used for treatment of hypertension, but the marketing authorization does of Intuniv[®] does not include that indication. Therefore, use of Intuniv for treatment of hypertension would be considered off-label use. The effects of Intuniv[®] for treatment of ADHD have been demonstrated in controlled trials in children and adolescents and in adult healthy volunteers (1).

Background and rationale of the current study

Intuniv[®] has not been studied in children under age 6 years, adults and the elderly. Therefore, in order to avoid any potential or unknown risks, it is currently not indicated for use in these populations.

Furthermore, there are identified risks of bradycardia, syncope, hypotension/decreased blood pressure, withdrawal blood pressure increase, sedative events, and weight increase. In order to minimize these identified risks, careful assessment of patients' blood pressure, weight and heart rate is required before initiation and during treatment of a patient with Intuniv[®].

To increase awareness and knowledge on these requirements, Shire Pharmaceuticals has developed and distributed educational materials to potential prescribers of Intuniv[®].

Shire Pharmaceuticals also proposed to conduct a drug utilization study as part of their risk management plan to assess effectiveness of these measures: The study described in this protocol has been designed to evaluate drug utilization and to monitor inappropriate use of Intuniv[®] in Europe, Shire Pharmaceuticals considers this study an important activity to evaluate whether Intuniv[®] is being prescribed within the approved SmPC and whether current risk minimisation measures are adequate.

Shire Pharmaceuticals has launched/ plans to launch Intuniv[®] from January 2016 onwards in Belgium, Denmark, Finland, Germany, Ireland, Netherlands, Norway, Spain, Sweden, and UK for treatment of ADHD. Expected launch dates are given in Table 2. In order to evaluate drug utilization and to monitor appropriate and potential inappropriate use of Intuniv[®] in Europe, Shire Pharmaceuticals proposed to conduct a drug utilization study as part of their risk management plan.

The indication for Intuniv[®] given in the Summary of Product Characteristics is as follows (1):

Intuniv[®] is indicated for the treatment of attention deficit hyperactivity disorder (ADHD) in children and adolescents 6 to 17 years old for whom stimulants are not suitable, not tolerated or have been shown to be ineffective. Intuniv[®] must be used as a part of a comprehensive ADHD treatment program, typically including psychological, educational and social measures.

Based on this label, inappropriate use of Intuniv® may include use in

- Patients with indications other than ADHD
- Children less than 6 years of age
- Adults
- Patients who did not have any first-line stimulant treatment prior to their first prescription of Intuniv®

• Patients with prescribed overdose of >7 mg/day, or of >4 mg/day for patients ≤12 years of age

In this drug utilization study, patient medical record data will be collected within a prescriber survey. Annual study reports will be generated by IQVIA and sent to Shire in 2019, 2020, 2021 and 2022.

This protocol specifies the objectives of the study, describes the methodology and data sources, outlines the plans for statistical analysis, and details the tasks and timelines for the project.

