9.3 VARIABLES

The survey aims to characterize patients who are prescribed Intuniv[®] and describe prescribing patterns of Intuniv[®] among physicians in European countries.

The following information is planned to be collected in the survey:

- Physician related data
 - o demographics
 - o setting
 - o prescriber's specialty
- patient characteristics
 - o age
 - o gender
 - o co-morbidities
- indication of use (diagnosis) according to WHO ICD 10 classification
- data on patterns of drug use
 - o first time user
 - o repeat user
 - o duration of treatment
 - o discontinuation of ADHD therapy
 - o switches (both from Intuniv[®] to other ADHD medications and other ADHD medications to Intuniv[®])
 - o dosing/ overdose (defined as daily dose of >7 mg or of >4mg in patients ≤12 years of age)
- use of Intuniv[®] as second line treatment after psychostimulant prescription at any time prior to the patient's first prescription of Intuniv[®]
- frequency of monitoring (physician) visits during the first year of therapy
- weight, blood pressure and heart rate during Intuniv[®] exposure

A detailed description of all variables and definitions is provided in Table 3 of the SAP for the survey protocol.

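### The no-prior-stimulant criterion for potential inappropriate use omits the label's route for patients unsuited to stimulants, and the listed variable cannot separate them

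*Protocol*

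**What the plan says.** Protocol Section 7 gives the indication as ADHD in "children and adolescents 6 to 17 years old for whom stimulants are not suitable, not tolerated or have been shown to be ineffective". The three conditions are alternatives.

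The same section then says that, on the basis of this label, inappropriate use "may include use in" five groups. One of them is "Patients who did not have any first-line stimulant treatment prior to their first prescription of" Intuniv. No exception is made for patients unsuited to stimulants. Section 8.2 repeats the group, in the same terms, as a focus of the first primary objective.

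Section 9.3 names the variable behind it: use of Intuniv "as second line treatment after psychostimulant prescription at any time prior to the" patient's first Intuniv prescription. No variable listed there records why a stimulant was not used or was stopped. For detail the section points elsewhere: "A detailed description of all variables and definitions is provided in Table 3 of the SAP for the survey protocol".

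Two places show how the list is meant to be read. The amendment log in Section 5 describes the Version 3.0 change to Section 7 as "Rewording of criteria for off-label use", and Section 11 says the survey is designed to allow off-label use to be evaluated.

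**The concern.** Intolerance and lack of effect both presuppose that a stimulant was tried. Unsuitability does not. A criterion that asks only whether a stimulant was ever prescribed therefore puts some patients who meet this clause of the indication into a group described as potentially inappropriate.

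The group is one of five named in the primary objective, and the secondary objective refers to compliance with the indication. Results go to the EMA every year (Section 12). If the row is read as off-label use, it mixes patients inside and outside the clause, and a larger sample would not separate them. If the reason is not asked during fieldwork, an anonymous survey that each physician can complete only once gives little chance of recovering it.

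**Working it through.** **The protocol's own figures.** Section 9.5.2 uses n = p(1 − p)z²/e². With p = 0.5 and z = 1.96:
- e = 0.05 gives 384.1 (stated: 384).
- e = 0.10 gives 96.04, rounded up to 97 (stated: 97).

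Both reproduce. The point concerns a definition and contradicts neither figure.

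**Label against criterion.**

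| Patient's stimulant history | Label's stimulant clause (Section 7) | Criterion in Sections 7 and 8.2, variable in 9.3 |
|---|---|---|
| Never given, unsuitable | Inside | Listed as potential inappropriate use |
| Never given, no label reason | Outside | Listed as potential inappropriate use |
| Given, not tolerated or ineffective | Inside | Counts as second-line use |
| Given, tolerated and effective, no label reason | Outside | Counts as second-line use |

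The first and last rows are misplaced, in opposite directions.

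**Size within the category.** Let u be the share of all patients with no prior stimulant, and s the fraction of those for whom stimulants were unsuitable. The share in this category that is outside the clause is u(1 − s). Reporting all of u as off-label overstates it by u − u(1 − s) = u × s, which is zero when s = 0 and positive otherwise.

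Neither u nor s is in the documents. Both ranges below are assumptions. The half-width is 1.96 × √(u(1 − u)/100), for 100 patients treated as independent.

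| u | s = 0% | 10% | 25% | 50% | 75% | 95% half-width, n = 100 |
|---|---|---|---|---|---|---|
| 10% | 0 | 1.0 | 2.5 | 5.0 | 7.5 | 5.9 |
| 20% | 0 | 2.0 | 5.0 | 10.0 | 15.0 | 7.8 |
| 30% | 0 | 3.0 | 7.5 | 15.0 | 22.5 | 9.0 |

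Entries are percentage points. At u = 20% and s = 50% the overstatement is 0.20 × 0.50 = 10 points, against a half-width of 1.96 × √(0.16/100) = 7.8. At the lower target of 50 patients the half-width is 1.96 × √(0.16/50) = 11.1, so there the same overstatement lies within sampling error.

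**Whole clause.** Let w be the share of all patients who had a prior stimulant but no label reason. The true share outside the clause is u(1 − s) + w, so using u misstates it by u × s − w. The sign depends on w, which the documents do not give either. In the 20%/50% example, w = 10% would cancel the error exactly.

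**The case against.** The case against has several parts, and much of it stands.

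- **The list is hedged.** Section 7 says inappropriate use "may include use in" these groups, which flags them for scrutiny and is not a rule applied to each patient. A reader might infer that every patient without a prior stimulant is classed as off-label. The protocol does not say that.
- **The objective is descriptive.** Section 8.2 asks for patients to be characterised with a focus on this group. The share with no prior stimulant is unbiased as a measure of itself; error enters only when it is labelled off-label use. This stands, but Sections 5 and 11 point towards that labelling.
- **The effectiveness verdict is separate.** A reader might infer that the row could make the risk minimisation appear to fail. Section 9.7.3 rests that verdict on physicians' answers to knowledge questions A2 to A5, and patient stimulant history does not enter it.
- **The SAP and questionnaire may already collect the reason.** Section 9.3 defers detail to SAP Table 3, Annex 1 lists the questionnaire separately, and Section 9.1 says the design was chosen so that data on compliance with the indication can be collected. Neither document was available for this check. If the reason is collected, no new question is needed, but the mismatch that the protocol itself fixes in Sections 7, 8.2 and 9.3 remains.

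**Conclusion.** The point holds as a mismatch of definition. The criterion is said to rest on the label but omits one of the label's three routes, and the variable listed in Section 9.3 cannot restore it. It also lets through a prior stimulant that worked and was tolerated.

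If the row is reported as off-label use, off-label use within that category is overstated by u × s. Under the assumed ranges that is 0 to 22.5 points. Zero is possible, and no single figure follows from the documents.

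Two stronger readings are not supported. One is that the off-label estimate as a whole is biased upward: for the whole stimulant clause the two misplacements oppose each other, so the net direction is open. The other is that this category could dominate an off-label total: the protocol defines no such composite.

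**What to change.** In Sections 7, 8.2 and 9.3:

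1. Record two items per patient: prior stimulant (yes/no), and the reason for Intuniv (stimulant not suitable, not tolerated, ineffective, or none of these).
2. Report no prior stimulant with stimulants not suitable, and no prior stimulant with no label reason, as separate rows.
3. Count as outside this clause of the indication only patients with none of the label reasons, whether or not they had a prior stimulant.
4. If the reason is not collected, report the row as no prior stimulant and not as off-label use.

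The cost is at most one closed question per patient, if the questionnaire does not already ask it, plus one or two table rows and the matching definition. The reason is reported by the physician, so it is open to the social desirability bias that Section 9.9.2 already acknowledges. The report should say so.
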